4.1 Estimated Power Analysis

A sample size of up to 24 subjects (5 randomized to Posiphen and 3 randomized to placebo per treatment group) is planned across 3-6 clinical research centers.

Table 1. Estimated Power Analysis

	n.active= 12	n.active= 15	n.active= 18
n.cont= 8	0.783	0.822	0.848
n.cont= 9	0.812	0.851	0.876
n.cont= 10	0.836	0.874	0.898

This serves as justification for our sample size estimate of 24. We expect that if dropouts are to occur, they will occur before the SILK™ studies at day 23-25 and can be replaced to allow the full sample size of 24 for SILK™ being achieved.

4.2 Study Populations

- a. **Enrolled Population:** All participants who consented to screening
- b. **Intention To Treat (ITT) Population:** list of all randomized participants
- c. **Modified Intention-to-Treat (mITT) Population:** Randomized participants who took at least one dose of study medication confirmed by compliance assessment and had at least one post randomization study visit
- d. **Per Protocol (completers):** Randomized participants who were
 - i. compliant through Confinement Visit,
 - ii. compliant to with 20% of dose 1 week prior Pre-Confinement, and
 - iii. completed the 36-hour sampling
- e. **Safety Population:** Randomized participants who:
 - i. took at least one dose of drug confirmed by compliance assessment

5 Statistical Analysis

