1 PROTOCOL SYNOPSIS

PROTOCOL TITLE	A Multicenter, Randomized, Double-Blind, Placebo-Controlled Ascending Dose Study to Evaluate the Safety, Tolerability, PK and PD Effects of Posiphen® in Subjects with Early AD
PROJECT DIRECTORS	[name]. and [name].
COORDINATING CENTER	Alzheimer's Disease Cooperative Study (ADCS)
STUDY DESIGN	
A Phase 1b multicenter, randomized, double-blind, placebo-controlled study evaluating safety, tolerability, PK and PD of 23-25 days exposure to multiple ascending doses of Posiphen in up to 24 participants with a clinical profile consistent with early AD including Mild Cognitive Impairment due to AD (MCI-AD) or Mild AD with the following planned doses:
 
 • 60 mg Once a Day (QD) (1x60mg) • 60 mg Twice a Day (BID) (2x60mg) • 60 mg Three Times a Day (TID) (3x60mg) 
Each dose group will include 8 subjects, 5 randomly assigned to Posiphen and 3 randomly assigned to placebo.
 
Each dose group will be completed and evaluated for safety and tolerability by the standing ADCS Data Safety Monitoring Board (DSMB). The ADCS DSMB will determine whether to approve dose escalation.
 
Subjects who do not tolerate study drug during the initial 3-week at-home treatment period will be discontinued and replaced by new subjects. If two subjects at a given dose are discontinued due to adverse events, no additional subjects will be added at this dose level until a safety review has been conducted. The safety committee will determine the appropriate dose level for additional subjects. The safety committee has the option to change the allocation of future patients to active drug versus placebo based on statistical advice to maintain an appropriate balance between placebo subjects and subjects on active drug.

DURATION OF STUDY PARTICIPATION	Each subject will have up to a 42-day screening period, followed by approximately 21-23 days of treatment at home, and an in-clinic visit that includes treatment and a 36-hour lumbar puncture (LP) Stable Isotope Labeling and Kinetics (SILK™) procedure.
SUMMARY OF INVESTIGATIONAL PRODUCT	Posiphen 60 mg QD, 60 mg BID or 60 mg TID, or placebo capsules taken orally for up to 25 days.

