7.6 Compliance

Site personnel will assess compliance based on the amount of study drug dispensed to and returned by the participants, together with any related information, including the administration of study drug by study staff during the confinement visit. Participants must take 80% of all doses at home (21-23 days) depending on the confinement visit date and should take at least 80% of all doses in the last week prior to the confinement visit. Site personnel will count capsules and evaluate compliance from the blister packs at the pre-confinement visit.

Prior to the pre-confinement visit, site personnel will also contact the participant and study partner to remind them of the dose regimen, in particular to ensure that the necessary level of compliance has been achieved to continue with the confinement visit procedures.

Site personnel will assess compliance at the pre-confinement visit and again at the time of admission for the confinement visit. If participants are found to be < 80% compliant for all doses at home and in the last week there is an insufficient level of compliance, the site must consult with the Project Directors (and/or Medical Monitor) regarding timing and conduct of the confinement visit procedures. It is possible that subjects will be discontinued early from the study due to insufficient drug compliance.

During the leucine infusion, participants must comply with a low leucine diet – 1500 mg or less of leucine per day. The kitchen on-site will have the responsibility of preparing low leucine meals meals/snacks and maintaining a food journal for each individual. (Refer to Appendix 4 for a sample low leucine menu).

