9.4 Day 14 Telephone Contact

A telephone call will be conducted at 14 ± 4 days from the baseline visit to assess for any changes in status, adverse events, or concomitant medications. Study medication compliance will be discussed and reminders given about the upcoming confinement visit. If there is an insufficient level of drug compliance (less than 80% overall and or less than 80% in the last week), the site must consult with the Project Directors and Medical Monitor regarding timing and conduct of the remaining confinement visit procedures. It is possible that subjects will be discontinued early from the study due to insufficient drug compliance.

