10 EARLY TREATMENT/STUDY DISCONTINUATION

The investigators at each site will make every reasonable effort to maximize subject retention. However, if an investigator removes a subject from treatment or study, or if a subject declines further treatment or study participation, an early discontinuation visit will be completed as soon as possible following discontinuation. The early discontinuation visit will contain the same assessments as the pre-confinement visit. If an in-person visit is not possible, site personnel will complete as much of the early discontinuation visit as possible by telephone.

Subjects who discontinue from the study prior to completing all protocol procedures may be replaced at the discretion of the Coordinating Center, in consultation with the Sponsor.

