5.1 Primary Aims

5.1.1 Aim 1

To determine the safety and tolerability of multiple ascending doses of Posiphen on subjects with early AD with up to 23-25 days of daily usage. Safety and tolerability will be summarized using the following tables, listing and figures:

- Vital signs
- Adverse events onset before randomization
- Adverse events onset after randomization
- AE overall
- AE by severity
- MedDRA coded AEs
- Percentage of AEs summarized by SOC
- Number of participants with at least one AE
- Number of AEs summarized by System Organ Class (SOC) and Preferred Terms (PT)
- Serious AEs (SAE) onset after randomization
- Death summary
- Hospitalization summary
- Safety Labs

5.1.2 Aim 2

To determine the PK of Posiphen and its metabolites in plasma and CSF of subjects with early AD treated with QD, BID and TID dosing regimens., samples will be analyzed at baseline time 0 pre first dose then at times 2H, 4H, 8H, 12 H, 16H, 20H and 24H post dose. Further doses are provided every 8 hours. Curves and area under the curve will be constructed for each of the three sequential dose cohorts of 60 mg daily, 60 mg BID, and 60 mg TID.

Standard PK parameters will be calculated for each subject, including AUC, C_{max} , t_{max} , $t_{1/2}$, V_{ss} . Dose-proportionality will be assessed on C_{max} and AUC statistics. Plasma concentrations will be displayed with time series plots including individual and means by dose. PK parameters summarized descriptively (N,

[figure not shown]
mean (SD) and 95% CI, median, min, max, and geometric mean (%CV) as appropriate) by each dose regimen. Accumulation ratio will be determined. CSF levels will be evaluated by dose levels and correlated where possible to blood levels.

The Charles River Lab in Montreal will analyze PK of Posiphen and its metabolites in Plasma and CSF. This will include Posiphen, N1-Desmethyl Posiphen (Phenserine) and N8-Desmethyl Posiphen (Phenserine). Phenserine is an enantiomer of Posiphen. The chromatographic assay used does not distinguish between the two enantiomers, so these metabolites represent the total amount of both.

5.1.3 Aim 3

To assess the PD effects on the FSR of Ab 40 using the SILK™ technique with multiple doses of Posiphen.

The schema for evaluating the Fractional Synthesis and Clearance Rate, the Absolute Synthesis and Clearance and Area under the concentration curve are presented in **Figure 1**.

The analytic techniques to calculate these values are undertaken by C2N.

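### The SAP Safety Population turns on a compliance check verifying a dose and has no default when that check is missing, so a dosed participant who stops early can be left out

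*SAP*

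**What the plan says.** SAP 4.2(e) defines the Safety Population as randomized participants who "took at least one dose of drug confirmed by compliance assessment". The mITT set in 4.2(c) carries the same condition and also requires a post-randomization visit. The SAP does not define the assessment, the standard of confirmation, or the handling of a participant for whom it is missing.

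The protocol describes compliance in several places:

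- Section 7.6: "Site personnel will assess compliance based on the amount of study drug dispensed to and returned by the participants, together with any related information". The same section says: "Site personnel will count capsules and evaluate compliance from the blister packs at the pre-confinement visit".
- Section 9.4, Day 14 call: "Study medication compliance will be discussed and reminders given about the upcoming confinement visit". In Appendix 1 this call (Day 14 ± 4) is the first scheduled compliance check.
- Section 10: the early discontinuation visit repeats the pre-confinement assessments, which under 9.5.1 include a compliance review. "If an in-person visit is not possible, site personnel will complete as much of the early discontinuation visit as possible by telephone".
- Section 7.5 requires drug containers to be returned but has no rule for those that are not.

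On replacement, the Synopsis says: "Subjects who do not tolerate study drug during the initial 3-week at-home treatment period will be discontinued and replaced by new subjects". Section 10 makes replacement of other early leavers discretionary.

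For primary Aim 1, SAP 5.1.1 says "Safety and tolerability will be summarized using the following tables, listing and figures" and lists the outputs. It names no analysis set, and the list has no display of discontinuations due to adverse events.

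**The concern.** A safety set should contain everyone exposed. Here membership depends on proof of exposure obtained by one route, and missing proof means exclusion. The participants most likely to lack it are those who stop in the first days at home, before any scheduled compliance check, and then withdraw or are lost (both foreseen in Protocol 10.1). Some of them will have stopped because of the drug. Because intolerant participants are replaced, a cohort can return to five active and three placebo without the analysis set showing that anyone left.

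Tolerability is part of primary Aim 1. With five active participants per dose, one omission is visible in the reported rate.

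**Working it through.** There is no figure in the plan to reproduce, because this is a definition. The check has two steps: who is excluded as written, and what one exclusion does to a rate.

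**Step 1. Four kinds of early stopper who took at least one dose**

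| Case | Compliance information | Status under SAP 4.2(e) |
|---|---|---|
| A. Attends the early discontinuation visit with the pack | Capsule count | Included |
| B. Keeps the pack but reports doses by telephone | Related information under Protocol 7.6 | Can be confirmed, but the SAP does not say that it must be |
| C. Reports an adverse event, then withdraws or is lost before any compliance assessment | None | Excluded, although the event is known |
| D. No contact at all after dispensing | None | Excluded, and no event is known |

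Case C is where the wording removes a known event. Case B is left to judgement. In case D the definition changes only the denominator.

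**Step 2. Effect of one case C**

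Inputs: 5 active participants per cohort and 3 cohorts (Protocol Synopsis and section 6; SAP section 3), so 15 active in all. Assumptions: one active participant is a case C who stopped for an adverse event; when replaced, the replacement is also active; no other active participant stops for an adverse event. Intervals are exact (Clopper-Pearson) 95%.

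| Setting | All dosed participants | As written |
|---|---|---|
| Cohort, replaced | 1/(5+1) = 16.7% (0.4 to 64.1%) | 0/5 = 0% (0 to 52.2%) |
| Cohort, not replaced | 1/5 = 20.0% (0.5 to 71.6%) | 0/(5−1) = 0/4 = 0% (0 to 60.2%) |
| Pooled active, replaced | 1/(15+1) = 6.3% (0.2 to 30.2%) | 0/15 = 0% (0 to 21.8%) |

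The intervals overlap widely. What changes is whether a tolerability failure appears in the table at all.

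**Step 3. What the remedy could cost**

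Suppose five active participants took drug and one stopped for an adverse event: 1/5 = 20.0%. If a sixth was dispensed drug, took none and was lost without record, counting that person as exposed gives 1/6 = 16.7%, a dilution of 3.3 percentage points.

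The documents give no rate of missing compliance assessments, so these figures are per event and cannot be turned into an expected bias.

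**The case against.** A reader might infer that confirmation requires a returned pack, so that anyone who keeps it is lost to the safety analysis. The documents do not support that. Section 7.6 extends the assessment to related information, and both the Day 14 call and the early discontinuation visit allow compliance to be discussed by telephone. Case B can be confirmed.

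A reader might also infer that the excluded participant vanishes from the primary safety aim. That goes too far. SAP 5.1.1 does not tie its tables to the Safety Population, and SAP 4.2 also defines a set of all randomized participants. Adverse events are still recorded on the eCRF and reported to the DSMB (Protocol 14.1 and 14.2). Nothing links dose escalation or the pause rule in Protocol 6.3 to SAP 4.2(e). Any harm is to the reported analysis, not to safety oversight.

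Nor does the rule select on outcome. It conditions on confirmation of dosing, and any link with adverse events is a possible correlation. The argument should not be extended to two excluded and automatically replaced participants either: after two AE discontinuations at a dose, no one is added until a safety review, which may alter the dose level or allocation.

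The strongest remaining objection is that contact revealing an AE discontinuation would usually also reveal that doses were taken. That makes case C uncommon. It does not remove it, because the SAP never says that an adverse event report, or a verbal report of dosing, satisfies the confirmation condition.

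**Conclusion.** The point holds in a narrow form. As written, a dosed participant with no compliance assessment is outside the Safety Population even when an adverse event was reported, and no default covers the gap. Separately, the denominator for primary Aim 1 is not stated.

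One such active participant would move a cohort's AE-discontinuation rate from 1/6 (17%) to 0/5 (0%). This assumes that SAP 5.1.1 uses the Safety Population (a reasonable reading, but not written), that the participant is replaced in the active arm, and that no one else in that arm stops for an adverse event. With the frequency unknown, this is a possible bias in a primary aim and not a demonstrated one. It is worth correcting before analysis because the change is cheap, but it does not by itself put the trial's safety conclusions in doubt.

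**What to change.** In SAP 4.2(e), delete the compliance-assessment condition. Include every randomized participant with evidence of at least one dose from any source: participant, study partner, telephone contact, adverse event record or capsule count. Count participants who were dispensed drug as exposed unless it is documented that they took none.

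In SAP 5.1.1, state that the post-randomization tables use this set by dose cohort and arm, including participants who were later replaced, and add a display of discontinuations due to adverse events on that denominator.

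The cost is a few lines of text and one display. The downside is that a participant who took nothing and was lost could be counted as exposed, slightly diluting event rates (the 20.0% to 16.7% example above). A listing of participants whose dosing is unconfirmed would make this visible.

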5.1 Primary Aims

5.1.1 Aim 1

To determine the safety and tolerability of multiple ascending doses of Posiphen on subjects with early AD with up to 23-25 days of daily usage. Safety and tolerability will be summarized using the following tables, listing and figures:

- Vital signs
- Adverse events onset before randomization
- Adverse events onset after randomization
- AE overall
- AE by severity
- MedDRA coded AEs
- Percentage of AEs summarized by SOC
- Number of participants with at least one AE
- Number of AEs summarized by System Organ Class (SOC) and Preferred Terms (PT)
- Serious AEs (SAE) onset after randomization
- Death summary
- Hospitalization summary
- Safety Labs

5.1.2 Aim 2

To determine the PK of Posiphen and its metabolites in plasma and CSF of subjects with early AD treated with QD, BID and TID dosing regimens., samples will be analyzed at baseline time 0 pre first dose then at times 2H, 4H, 8H, 12 H, 16H, 20H and 24H post dose. Further doses are provided every 8 hours. Curves and area under the curve will be constructed for each of the three sequential dose cohorts of 60 mg daily, 60 mg BID, and 60 mg TID.

Standard PK parameters will be calculated for each subject, including AUC, C_{max} , t_{max} , $t_{1/2}$, V_{ss} . Dose-proportionality will be assessed on C_{max} and AUC statistics. Plasma concentrations will be displayed with time series plots including individual and means by dose. PK parameters summarized descriptively (N,

[figure not shown]
mean (SD) and 95% CI, median, min, max, and geometric mean (%CV) as appropriate) by each dose regimen. Accumulation ratio will be determined. CSF levels will be evaluated by dose levels and correlated where possible to blood levels.

The Charles River Lab in Montreal will analyze PK of Posiphen and its metabolites in Plasma and CSF. This will include Posiphen, N1-Desmethyl Posiphen (Phenserine) and N8-Desmethyl Posiphen (Phenserine). Phenserine is an enantiomer of Posiphen. The chromatographic assay used does not distinguish between the two enantiomers, so these metabolites represent the total amount of both.

5.1.3 Aim 3

To assess the PD effects on the FSR of Ab 40 using the SILK™ technique with multiple doses of Posiphen.

The schema for evaluating the Fractional Synthesis and Clearance Rate, the Absolute Synthesis and Clearance and Area under the concentration curve are presented in **Figure 1**.

The analytic techniques to calculate these values are undertaken by C2N.

The primary outcome measure of Fractional Synthesis Rate (FSR) of Abeta 40 will be compared across all Posiphen treated groups to placebo. A linear regression model will be used to evaluate treatment effects on the FSR Abeta 40, with age and gender as covariates. Quality control of samples for the FSR 40 will be ascertained to determine sufficiency of the sample values prior to this regression analysis.

A secondary analysis will test for possible dose group by treatment interaction.

Exploratory analyses will include PK AUC correlation to Abeta 40 FSR and other SILK measured analytes (Abeta 38, 42, ratio 42/40, total Abeta peptides) including absolute synthesis and clearance.

C2N will analyze Beta Amyloid 40 (Ab40).

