3.2 Summary of Clinical Findings

Three Phase 1 studies have been conducted with Posiphen (Annovis Bio, Inc. 2019). The first was an SAD study in healthy volunteers; the second was an MAD study in healthy volunteers, and the third one was a PK/PD study of CSF obtained from mild cognitively impaired participants.

In the multiple ascending dose trial, Posiphen was administered orally in doses of 20, 40, and 60 mg 4 times a day (QID). The first two treatments were administered for 7 days, and the third, for 10 days. Single doses were given on the first and last day to determine the pharmacokinetics of the drug. In general, the drug was well tolerated, resulting in no serious or severe adverse events and only one premature discontinuation, a subject in the 60 mg group discharged because of nausea, vomiting, dizziness and “feeling warm.” The incidence of adverse events, all of either mild or moderate severity also occurred with similar frequency in the placebo group. The most common AEs were dizziness, headache, and nausea/vomiting.

Posiphen was absorbed rapidly after oral administration, achieving maximum plasma and CSF concentration (C_{max}) within 1.2 - 1.5 hours. For the 40 and 60 mg doses, with fully defined plasma profiles, the mean terminal $t_{1/2}$'s were 3.80 ± 0.88 and 5.23 ± 1.24 hours, respectively after a single dose and 3.53 ± 1.03 and 4.104 ± 0.91 hours, respectively, after repeat dosing. The half-life ($t_{1/2}$) of the plasma concentrations at the lower doses could not be calculated accurately. The C_{max} increased disproportionately with dose (24, 144, and 2310 ng.h/mL after a single dose of 20, 40, and 60 mg, respectively and 110, 134, and 2101 ng.h/mL after multiple doses of 20, 40, and 60 mg, respectively).

In the proof of mechanism of action study, the PK of Posiphen was measured after 10 days of administration (4x60 mg) over 12 hours in CSF and plasma of the AD participants. The PD of a number of biomarkers was compared for 12 hours before the first dose at day 0 and after the last dose at day 11 of Posiphen administration. We found that the plasma concentrations of Posiphen overlapped with the plasma concentrations found in the MAD study. In this study, the N1 metabolite reached about 10 to 15%, while the level of the N8 metabolite reached about 20 to 25% of the Posiphen levels measured in plasma.

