6.3 Safety and Tolerability Analysis

Safety and tolerability will be assessed with physical examinations, vital signs, clinical laboratory values, use of concomitant medications, and AE reports. The frequencies of adverse events, serious adverse events and laboratory abnormalities between the participants across the three groups will be compared. The severity of cholinergic adverse events will be carefully evaluated taking the criteria in Appendix 5 into consideration (modified from Common Terminology Criteria for Adverse Events (CTCAE) version 4.03) as there is potential for an interaction between Posiphen and Donepezil through the inhibition of AChE, thereby resulting in increased cholinergic activity.

Each dose group will be completed and evaluated for safety and tolerability by the standing ADCS DSMB before the next dose group is initiated. Drug administration at the next higher dose level may not proceed until written confirmation is provided from the ADCS DSMB indicating that the results of the previous dose level were evaluated and that it is permissible to proceed to a higher dose level.

Subjects who do not tolerate study drug during the initial 3-week at-home treatment period will be discontinued and replaced by new subjects. If two subjects at a given dose are discontinued due to adverse events, no additional subjects will be added at this dose level until a safety review has been conducted. The ADCS DSMB will determine the appropriate dose level for additional subjects. The ADCS DSMB has the option to change the allocation of future patients to active drug versus placebo based on statistical advice to maintain an appropriate balance between placebo subjects and subjects on active drug.

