 - a. Collect CSF (6 mL) and blood (10mL) every 2 hours at the following time points: 0, 2, 4, 6, 8, 10, 12, 14, 16, 18, 20, 22, 24, 26, 28, 30, 32, 34 and 36 hours; all collection times should be calculated from the start of the heavy leucine infusion. Samples should be in separate tubes and sent to the ADCS Biomarker Core
NOTE: If unable to obtain a total of 6 mL CSF at any given collection time (e.g., due to participant headache or participant’s CSF production level) please obtain the maximum amount possible and notify ADCS Clinical Operations
 - b. At 0 hours, an additional 1-2 ml CSF (or volume per Local laboratory requirements) should be sent ambient to the local laboratory for protein, glucose, and cell counts
 - c. Perform safety monitoring every 4 hours while the subject is awake. This includes questions about any symptoms in relation to the CSF catheter (including potential adverse events such as leg or back pain, dizziness or headaches) and vital sign monitoring. Participants also should be asked about pain, redness or swelling at the IV site in the arm
 - d. Administer assigned study drug (will vary based on blinded treatment assignments) every 8 hours – at 8, 16, 24, and 32 hours
 - e. Provide low leucine meals and snacks as needed during the duration of the heavy leucine infusion; return to normal diet after completion of the infusion (Refer to Appendix 4, Sample Low Leucine Menu)
 - f. Subjects remain at bedrest throughout the CSF sampling period of 36 hours. They are allowed to use a bedside commode for toileting
8. 36 hours after the start of the heavy leucine infusion, collect the final blood and CSF samples. An extra 9mL of whole blood should be sent to the central lab for the metabolic panel and a CBC/Diff. An extra 2mL of CSF should be sent to the local lab for protein, glucose, and cell counts
9. Remove the blood and LP catheters
10. Perform final safety monitoring, a brief physical and a brief Neurological Exam

If the subject experiences intolerable AE(s) that require early discontinuation of the sampling procedures and removal of the LP catheter, contact the Medical Monitor and Project Directors as soon as possible to discuss the situation. If feasible, the standard 12-hour observation and discharge procedures should be followed to allow for management and follow-up on the adverse events.

Phase 3: 12-Hour Observation

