14.1 Definition

An AE is defined as per the US Code of Federal Regulation, Title 21, Part 312.32 [<http://www.accessdata.fda.gov/scripts/cdrh/cfdocs/cfcfr/cfrsearch.cfm?fr=312.32>]. An AE is any untoward medical occurrence associated with the use of a drug in humans, whether or not considered drug related.

Collection of adverse events will begin once informed consent is signed and will continue until the follow-up phone call performed on the day after discharge. Adverse events include but are not limited to: (1) worsening or change in nature, severity, or frequency of conditions or symptoms present at the start of the study; (2) Subject deterioration due to primary illness; (3) intercurrent illness; and (4) drug interaction. An abnormal laboratory value will only be reported as an AE if the investigator considers it clinically significant, or if it leads to the subject being withdrawn from the study.

The investigator should attempt to establish a diagnosis of the event based on signs, symptoms, and/or other clinical information. In such cases, the diagnosis should be documented as the AE and not the individual signs or symptoms. Symptoms and conditions present at the beginning of the study will be characterized, so that AEs can be defined as any new symptom, or any increase in frequency or severity of an existing symptom. Adverse events should be described with medical terminology so that the event can be matched against a medical coding dictionary, such as MedDRA (Medical Dictionary for Regulatory Activities).

Investigators should report their assessment of the potential relatedness of each AE to the protocol procedure, and to the investigational product, and/or drug delivery system used in the protocol.

Following questioning and evaluation, all AEs, whether determined to be related or unrelated to the study drug by a medically qualified site PI or clinician must be documented in the subject's records, in accordance with the investigator's normal clinical practice, and on the AE electronic case report form (eCRF).

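### SAP 5.1.1 plans no AE table by study phase or by relatedness, so headache and dizziness from the 36-hour catheter procedure dilute the drug-placebo comparison for those terms

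*SAP*

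**What the plan says.** - SAP 5.1.1 lists the Aim 1 displays. AEs are split into "Adverse events onset before randomization" and "Adverse events onset after randomization". The other AE displays are overall, by severity, by MedDRA term and system organ class, participants with any AE, SAEs, deaths and hospitalizations. None is by period after randomization, and none is by relatedness.
- Protocol 14.1 starts AE collection at consent, and it "will continue until the follow-up phone call performed on the day after discharge". The whole catheter stay is inside this window. Dosing also continues through sampling (Protocol 7.2 and 9.5.2).
- For the earlier multiple-dose study, Protocol 3.2 states: "The most common AEs were dizziness, headache, and nausea/vomiting".
- Protocol 9.5.2 has staff ask about catheter symptoms every 4 hours while the subject is awake, "including potential adverse events such as leg or back pain, dizziness or headaches". Protocol 5.3 gives post-lumbar puncture headache as the most frequent procedure AE and puts the rate needing a blood patch at about 10% in older people.
- Protocol 14.1 also states: "Investigators should report their assessment of the potential relatedness of each AE to the protocol procedure, and to the investigational product". No SAP display uses these fields.
- Under Protocol 6.3, subjects who do not tolerate drug at home are discontinued and replaced. Under SAP 4.2 they remain in the Safety Population once one dose is confirmed.

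**The concern.** Two exposures with overlapping symptoms share one set of tables. A subject with headache on day 10 of drug and a subject with headache two hours after catheter removal count alike. All arms are meant to have the procedure, so its events raise the rate in every column and compress the difference between them.

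Ascertainment adds to this. Between first dose and admission, scheduled AE review consists of the day-14 call and the pre-confinement visit. During sampling it is every 4 hours. Symptoms are sought hardest when the procedure is a competing cause.

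The plan already recognises the principle. Events before randomization, which include any after the screening lumbar puncture, are tabulated separately. The longer catheter procedure gets no such separation.

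At stake is how clearly the Aim 1 tables show the drug's own contribution to headache and dizziness.

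**Working it through.** The plan states no AE rate, precision or power for Aim 1, so there is no figure to reproduce.

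**Inputs from the documents.** 15 active (5 per dose) and 9 placebo (SAP 4). Procedure rate q of about 10% for headache needing a blood patch (Protocol 5.3). The rate of any procedural headache, and of procedural dizziness, is not given.

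**Assumptions.** At-home rates of 40% active and 10% placebo for an overlapping symptom, and q of 30% and 50% as higher values. The procedure acts equally in both arms and independently of drug, and all drug-caused events start at home.

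**Step 1: dilution.** If p is the at-home rate, the pooled incidence is 1 - (1 - p)(1 - q). Subtracting the arms gives:

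pooled risk difference = (1 - q) × (p_active - p_placebo)

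| q | Active | Placebo | Risk difference | Risk ratio |
|---|---|---|---|---|
| 0 (at-home only) | 40% | 10% | 0.30 | 4.0 |
| 10% (documented floor, headache) | 46% | 19% | 0.27 | 2.4 |
| 30% (assumed) | 58% | 37% | 0.21 | 1.6 |
| 50% (assumed) | 70% | 55% | 0.15 | 1.3 |

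Example for q = 30%: active 1 - 0.60 × 0.70 = 0.58; placebo 1 - 0.90 × 0.70 = 0.37; difference 0.21 = 0.70 × 0.30. The proportional loss is q whatever at-home rates are assumed, and the sign does not change.

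**Step 2: how much this matters beside sample size.** Exact two-sided Fisher power at 0.05 for 15 v 9 is 0.19 unpooled, then 0.16, 0.11 and 0.08 at q = 10%, 30% and 50%. This is illustrative only, because the SAP specifies no AE test. It shows that detection is weak before any pooling.

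**Step 3: unequal exposure to the procedure.** A subject who stops at home counts in the Safety Population but never has the catheter. With no drug effect, the pooled rate in an arm is q × (number having the catheter ÷ number in the Safety Population). Assume 4 active subjects stop at home and are replaced, and no placebo subject does:

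- Active: 15 of 19 have the catheter. At q = 30%, 0.30 × 15/19 = 0.237, or 24%.
- Placebo: 9 of 9 have it, so 0.30 × 9/9 = 30%.

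The table would show a 6-point difference in favour of active that comes only from who reached the catheter. At q = 10% the same calculation gives 8% v 10%. With a phase-specific denominator (15 and 9), both arms show q.

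**Step 4: event-level displays.** Where AEs are shown as percentages of all AEs by organ class, catheter events enter both numerator and denominator. The share of every other class then falls as procedural events accumulate.

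**The case against.** A reader might infer that the procedure masks a cholinergic signal, nausea above all. The documents do not support that. Neither Protocol 5.3 nor the symptom list in Protocol 9.5.2 names nausea as a catheter risk, and none of the five cholinergic terms in Appendix 5 (nausea, vomiting, diarrhea, anorexia, fatigue) is listed there. The documented overlap is headache and dizziness. Nor should the size be argued from the 40% nausea rate in the earlier single-dose study, which arose at 160 mg, whereas each dose here is 60 mg.

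Other points on that side:

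- In the earlier single-dose study, dizziness was 21.7% on Posiphen and 25.0% on placebo, so there may be little contrast to dilute. This stands as a caution about size. It is not a reason to leave the sources unseparated.
- Aim 1 is descriptive, and numbers limit it more than pooling does. This stands.
- Protocol 14.1 asks for the diagnosis to be recorded in place of symptoms, so a diagnosed post-puncture headache may be recorded under its own term. This helps in part. It does not help for undiagnosed headache, for dizziness, or for displays that are not by term, such as participants with any AE.
- Dose escalation rests on DSMB review of each dose group, not on these end-of-study tables. This also stands: the point concerns reporting of Aim 1, not escalation.

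A reader might also infer that the at-home phase should become the main tolerability comparison. The documents do not support this either: dosing continues in confinement, and Aim 1 covers the full 23-25 days.

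**Conclusion.** The point holds as a gap in the planned displays; the data needed to close it are collected. For headache and dizziness, the post-randomization tables mix drug and procedure and shrink the drug-placebo risk difference by a factor (1 - q). That is about 10% at the documented floor for headache and 30-50% only if q is assumed to be that high. This is dilution, not masking, and with equal exposure to the procedure it does not reverse direction. A spurious difference can arise if at-home stops are uneven between arms, as in the assumed 24% v 30% example.

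These sizes rest on an equal q in both arms, independence from drug effect, and drug events starting at home. Drug events that start in confinement would make the at-home table incomplete, so neither phase is sufficient alone.

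**What to change.** In SAP 5.1.1, keep the overall post-randomization tables and add:

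1. AE tables by onset phase: (a) first dose to catheter insertion and (b) catheter insertion to the 24-hour call. The denominator for each is the number of subjects entering that phase.
2. Columns for pooled placebo, QD, BID, TID and all Posiphen.
3. A table by recorded relatedness to drug and to procedure.

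Report both phases beside the overall table, with neither designated as the main comparison.

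The cost is some programming and a few more tables, several with small counts per dose. No new data are needed: the relatedness assessments are already required by Protocol 14.1, and onset timing is already needed for the split at randomization.
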